| Amendment number | Date of amendment | Rationale of amendment | Impact to statistical analysis and descriptions |
|------------------|-------------------|--|---|
| #1 | June, 2019 | The PK analyses were planned but not conducted in the combination arm which was stopped since the optimal combination dose could not be determined. Only a few subjects were enrolled in the combination arm who agreed to PK sample collection and due to the limited samples collected, the PK TLGs will not be generated. | The PK TLG will not be produced. |
| #2 | Mar 19, 2020 | The AESI list had been updated to reflect the new search paths. | The AESI related tables and listings will be updated. |
| | | | |
| | | | |

1. LIST OF ABBREVIATIONS

Table 1: Abbreviations and Specialist Terms

| | |
|-------|--|
| AE | adverse event |
| AML | acute myelogenous leukemia |
| ATC | Anatomical Therapeutic Chemical |
| BMI | body mass index |
| BSA | body surface area |
| CI | confidence interval |
| CR | complete remission |
| CRF | case report form |
| CTCAE | Common Terminology Criteria for Adverse Events |
| DMC | Data management committee |
| ECG | Electrocardiogram |
| ECOG | Eastern Cooperative Oncology Group |
| eCRF | electronic case report form |
| ESA | erythropoiesis-stimulating agents |
| FCBP | female of child-bearing potential |
| HI | hematologic improvement |
| HI-E | hematologic improvement erythroid |
| HI-N | hematologic improvement neutrophil |
| HI-P | hematologic improvement platelet |
| HRQoL | health-related quality-of-life |
| IC | informed consent |
| INT-1 | intermediate-1 |
| IP | Investigational Product |
| IPSS | International Prognostic Scoring System |
| ITT | Intent to treat |
| IVRS | Interactive Voice Response System |
| IWG | International Working Group |

| | |
|---------|--|
| KM | Kaplan-Meier |
| mCR | Marrow CR |
| MDS | myelodysplastic syndromes |
| MedDRA® | Medical Dictionary for Regulatory Activities |
| mITT | modified intent to treat |
| NCI | National Cancer Institute |
| OS | overall survival |
| PD | pharmacodynamic/pharmacodynamic |
| PK | pharmacokinetics/pharmacokinetic |
| PR | partial remission |
| pRBC | packed red blood cell |
| QD | once daily |
| RBC | red blood cell |
| ROW | rest of world |
| SAP | statistical analysis plan |
| SAS | Statistical Analysis Software |
| SC | subcutaneously/subcutaneous |
| SD | stable disease |
| SOC | system organ class |
| TEAE | treatment emergent adverse event |
| WBC | white blood cell |
| WHO | World Health Organization |

2. INTRODUCTION

This statistical analysis plan (SAP) describes the scope and methodologies of statistical data analyses and presentations of the analytical results for Celgene protocol CC-486-MDS-006: “A Phase 2, International, Multicenter, Randomized, Open-label, Parallel Group Study to Evaluate the Efficacy and Safety of CC-486 (Oral Azacitidine) Alone and in Combination With Durvalumab (MEDI4736) in Subjects With Myelodysplastic Syndromes Who Fail to Achieve an Objective Response to Treatment With Azacitidine for Injection or Decitabine.”

This SAP contains brief descriptions of the investigational plan, study subject disposition, demographics and baseline characteristics of study subjects, treatment exposure analysis, concomitant medication analysis, and general statistical considerations for the analysis of efficacy and safety data.

The study consists of four study phases: Screening, Safety Run-in, Randomized Treatment, and Follow-up. The objective of the safety run-in phase is to determine the dose regimen for the monotherapy with CC-486 and the combination therapy with CC-486 + durvalumab using the 3+3 experimental design. After the determination of dose regimen for monotherapy or combination therapy, the study will enter the randomization treatment phase utilizes the Simon’s two-stage design method for four patient cohorts, namely, the stable disease (SD) cohort treated with CC-486, the progressive disease (PD) cohort treated with CC-486, the SD cohort treated with CC-486 + durvalumab, and the PD cohort treated with CC-486 + durvalumab.

The analysis will be performed for the first stage initially to determine whether a cohort should continue to the second stage. Further analysis at the end of second stage will be conducted for the cohorts which enter the second stage of the study. Subjects will be followed for potential safety issues after they leave the safety run-in or treatment phase. The analytical results of efficacy and safety data for all cohorts will be presented together in a report with tables and listings.

This SAP will be finalized and signed-off prior to the clinical database is locked for the interim analysis or the first stage clinical data analysis, whichever occurs sooner, of any patient cohort. All statistical analyses detailed in this SAP will be conducted using Statistical Analysis Software (SAS)[®] Version 9.3 or higher.

3. OBJECTIVES

3.1. Primary Objective

The primary objective of this study is to investigate the efficacy of CC-486 as monotherapy, and in combination with anti-PD-L1 monoclonal antibody, durvalumab (MEDI4736), in subjects with MDS that did not respond to the most recent treatment with an injectable hypomethylating agent (HMA – azacitidine for injection or decitabine), or were unable to tolerate treatment with an injectable HMA.

3.2. Secondary Objectives

The secondary objectives of the study are to:

- Assess the safety and tolerability of CC-486 alone and in combination with durvalumab, as treatment for MDS.
- Describe the clinical relevance of objective hematologic and/or biologic responses associated with treatment with CC-486 alone and in combination with durvalumab.
- Evaluate the impact (if any) of durvalumab on the pharmacokinetics of CC-486 and CC-486 on durvalumab in subjects with MDS.

CCI [REDACTED]

- [REDACTED]
- [REDACTED]
- [REDACTED]
- [REDACTED]

4. INVESTIGATIONAL PLAN

4.1. Overall Study Design and Plan

This is a Phase 2, international, multicenter, randomized, parallel group, open-label study consisting of 4 study phases: *Screening*, *Safety Run-in*, *Randomized Treatment*, and *Follow-up*.

Safety Run-In Phase:

Safety Run-in will use the 3+3 design to explore the possible dose regimen for the monotherapy and combination therapy as well as the corresponding safety and tolerability profiles. Safety run-in will be conducted in sequential order with monotherapy first and then the combination therapy. The number of subjects needed for this phase will depend on the safety and tolerability findings

Randomized Treatment Phase:

The randomized treatment phase of the study will be conducted in 2 stages using Simon's two-stages design. Following identification of dose and schedule in the safety run-in of a treatment arm, enrollment for Stage 1 of the treatment phase may begin.

Eligible subjects will be randomized to one of two open treatment arms. In the event that combination therapy cohorts are not ready to enroll for this phase, the available subjects will be enrolled into the monotherapy cohorts. The randomization with 1:1 ratio will start when safety run-in phase is finished for both monotherapy and combination therapy arms. In the event that one arm has completed enrollment, all available subjects thereafter will be enrolled into the other arm. The randomization will be stratified according to subject's disease status, namely, Stable Disease (SD) or Progressive Disease (PD), at study entry.

Based on subject's disease status and the treatments, there will be four cohorts: (1) SD with Monotherapy, (2) PD with Monotherapy, (3) SD with Combination therapy, and (4) PD with Combination therapy.

During Stage 1, if a cohort is awaiting the decision to continue to Stage 2 pending on the response evaluation while the other cohort of the same patient classification is open for enrollment, available patients will be assigned to the cohort with open enrollment without randomization. If both cohorts of the same patient classification are waiting for response evaluations, enrollment of that patient classification will be temporarily halted.

The total number of subjects for the randomized treatment phase will range from approximately 64 (at Stage 1) to 164 (Stage 1 plus Stage 2) for the four subject cohorts. More subjects can potentially be recruited for replacement of non-evaluable subjects, if needed. Details can be found in the Sample Size section.

PK Sampling:

Blood samples for pharmacokinetic analysis will be collected from approximately 10-12 evaluable subjects received the combination treatment arm at selected sites. This will enable assessment of drug-drug interactions.

Follow-up Phase

All subjects who receive at least one dose of CC-486 (durvalumab) in the safety run-in or randomized treatment phase and discontinue treatment for any reason will be followed for at least 28(90) days after their last dose of CC-486 (durvalumab) for the assessment of safety-related parameters. After the 28(90)-day period for CC-486 (durvalumab), only SAEs made known to the investigator that are suspected of being related to treatment with CC-486 (durvalumab) need to be reported.

A 28(90)-day follow-up visit will be conducted 28(90) (± 3) days following the last dose of CC-486 (durvalumab) or during the final treatment phase study visit (whichever date is later) for assessment of the safety-related parameters.

Subjects in follow-up will then be contacted every 3 months from the date of the 28(90)-day follow up visit for CC-486 (durvalumab) until death, loss-to follow-up, withdrawal of consent to further follow-up, or study closure to collect information related to survival, subsequent MDS-related therapies, and disease progression to AML. This will continue until the last active subject completes approximately 12 months of treatment and/or follow-up unless additional follow-up is needed to evaluate time-to-event endpoints. Follow-up contacts will routinely be conducted by telephone unless special circumstances exist.

Study Closure

The study is expected to close when the last subject completes approximately 12 months of treatment and/or follow-up, unless additional follow-up is needed to analyze time-to-event endpoints.

4.2. Study Endpoints

4.2.1 Primary Endpoint

The primary endpoint of this study is the overall rate of objective response (ORR) to treatment with CC-486 as the monotherapy and treatment with CC-486 and durvalumab as combination therapy. The ORR is defined as the proportion of subjects achieving an objective response (HI, PR, CR, or marrow CR) based on modified International Working Group (IWG) 2006 criteria.

4.2.2 Secondary Endpoint(s)

The secondary endpoints of this study are:

- Overall survival;
- Time to onset of responses;
- Duration of responses;
- Progression free survival (time to disease progression or death from any cause);
- Proportion of subjects with progressive disease at baseline achieving Stable Disease, as well as time to achieving stable disease and duration of stable disease;
- The proportion of subjects progressing to AML and time to AML progression;
- Safety and tolerability (type, frequency, severity of AEs and relationship of AEs to CC-486 and/or durvalumab; monitoring for disease progression to AML, as well as immune- and infusion-type reactions);

- Serum/plasma PK parameters for durvalumab and CC-486, such as maximum observed concentration (C_{max}), area under the concentration-time curve (AUC), time to maximum concentration (T_{max}), terminal half-life ($t_{1/2}$), clearance (CL/F) and volume of distribution (V_z/F).

CCI

[REDACTED]

4.3. Sample Size

The sample size required will be identical for each treatment arm in each cohort and is estimated using the optimal design of the Simon's two-stage design method ([Simon, 1989](#)). The null hypothesis of the response rate will be tested against a one-sided alternative.

For each cohort, the null hypothesis of the response rate ($H_0 : p \leq 0.125$) will be tested against the alternative hypothesis of the response rate ($H_1 : p \geq 0.27$) with a type I error rate of 10% and 80% power. During the first stage, 16 subjects will be accrued. If there are 2 or fewer responses in these 16 subjects, the cohort will be stopped, and no further recruitment will be needed. Otherwise, 25 additional subjects will be accrued for a total of 41 subjects per cohort. If 8 or more responses are observed in these 41 subjects, the null hypothesis will be rejected.

For each cohort, in addition to the evaluation of treatment responses based on objective response criteria, the quality of responses will also be considered for the decision whether to continue the cohort to the second stage of the study. *Quality of response* will be assessed based on the

magnitude of hematologic and biologic responses observed in individual subjects, with special consideration for response duration.

CELGENE PROPRIETARY INFORMATION

5. GENERAL STATISTICAL CONSIDERATIONS

5.1. Reporting Conventions

Summary tables, listings, and any supportive SAS output will include a “footer” of explanatory notes that will indicate, at a minimum, the program source (e.g., SAS program name, including the path, that generates the output) and data extraction date (e.g., the database lock date, run date). The purpose of the data extraction date is to link the output to a final database, either active or archived, that is write-protected for replication and future reference. An output date will also appear on each output page and will indicate the date the output was generated by the analysis program. Individual source listing will display all the relative values supporting corresponding tables and figures.

Descriptive summaries for continuous data will include the following statistics: N, mean, standard deviation (SD), minimum, median, and maximum, unless specified otherwise. Categorical summaries for discrete data will include the frequency (count) and percentage at each discrete value (category), unless specified otherwise.

5.1.1. Calculation Using dates

Calculations using dates (e.g., subject’s age or relative day after the first dose of study medication) will adhere to the following conventions:

- Study days after the start day of study drug will be calculated as the difference between the date of interest and the first date of dosing of study medication (dstart) plus 1 day.
 - The generalized calculation algorithm for relative day is defined as:
 - a. study day = [(target date – dstart) + 1], if (target date >= dstart).
 - b. study day = [(target date – dstart)], if (target date < dstart).
 - Note: Study Day 1 is the first day of treatment of study drug. Negative study days indicate the observations were obtained before the first dose of study drug.
 - Partial date for the first study drug dosing will be imputed according to the criterion in Appendix A of section 14.1. All effort should be tried to avoid incomplete start date of study drug.
- Age (in years) is defined as: [Age = date of consent – date of birth + 1]/365.25 with rounding.
 - Calculation of age should base on the dates in clinical database, otherwise, the calculation will base on dates from CRF or IVRS.

- Partial birth date will be imputed as follows: impute missing day as 15th of the month; impute missing month as July. If birth year is missing, age will be recorded as missing.
- Algorithm to convert DAYS to WEEKS: $WEEKS = DAYS / 7$.
- Algorithm to convert DAYS to MONTHS: $MONTHS = DAYS / 30.4167$.

5.1.2. Calculation of Cycles

The start date of each treatment cycle will be calculated based on study drug exposure records for each patient. The start date of the first cycle will be the date when the subject receives the first dose of study drug. Once the start date is calculated, the end date of each cycle is calculated as the day before the start date of the following cycle. For the last cycle, the end date will be calculated as the start date plus prescribed cycle length, or the death date, whichever is earlier. The cycle number will be calculated based on the cycle window set by their start and end dates.

5.2. Analysis Populations

5.2.1. Intent-to-Treat Population

The intent-to-treat (ITT) population will include all enrolled subjects who received at least one dose of IP.

5.2.2. Modified Intent-to-Treat Population

The modified intent-to-treat (mITT) population includes all ITT subjects who have at least one post-baseline efficacy assessment performed, met all inclusion/exclusion criteria, and received a minimum of one cycle of treatment.

5.2.3. Safety Population

The safety population includes all enrolled subjects who have received at least 1 dose of IP and had at least 1 post-dose safety assessment.

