10.2.3. Safety Population

The safety population will include all enrolled subjects who have received at least 1 dose of IP and had at least 1 post-dose safety assessment.

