10.7. Safety Analysis

The safety population will be used for all safety evaluations.

Adverse events will be coded using Medical Dictionary for Regulatory Activities (MedDRA). Adverse event listings will include the verbatim term and the MedDRA preferred term. Adverse events will be summarized by worst severity grade. Adverse events, as well as treatment-emergent AEs, will be summarized by system organ class, and preferred term. Adverse events leading to death or to discontinuation from treatment, events classified as NCI CTCAE (Version 4.03) Grade 3 or Grade 4, adverse events related to IP, serious adverse events and Adverse Events of Special Interest (AESI) will be summarized separately.

Clinical laboratory results will be summarized descriptively and will include a display of change from baseline. Laboratory values outside of the normal ranges will be identified. Clinically significant hematologic and non-hematologic laboratory abnormalities that meet Grade 3 or Grade 4 criteria according to the CTCAE will be listed and summarized.

Vital sign measurements will be listed for each subject at each visit. Descriptive statistics for vital signs, both observed values and changes from baseline, will be summarized.

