10. EFFICACY ANALYSIS

All efficacy analyses will be performed on the ITT population. Supportive efficacy analyses will also be performed using the evaluable population.

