11. SAFETY ANALYSIS

The purpose of this section is to define the safety analysis for the study. All summaries of safety data will be conducted using the safety population. Descriptive statistics will be provided by disease cohort and treatment arm.

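### Safety-set membership turns on an undefined post-dose safety assessment, so a dosed subject counted in ITT survival may be missing from the adverse event and death summaries

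*SAP*

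**What the plan says.** SAP 5.2.1 builds the efficacy set on dosing alone: "The intent-to-treat (ITT) population will include all enrolled subjects who received at least one dose of IP". SAP 5.2.3 also requires a dose for the safety set, but adds a second condition: "and had at least 1 post-dose safety assessment". Protocol 10.2.3 has the same requirement ("had at least 1 post-dose safety assessment"), so the two documents agree.

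The two sets serve different parts of the report. SAP 10 states: "All efficacy analyses will be performed on the ITT population". That includes overall survival, which SAP 10.2.1 counts from first dose to death from any cause. SAP 11 states: "All summaries of safety data will be conducted using the safety population". Protocol 10.7 is at least as broad: "The safety population will be used for all safety evaluations". The death summaries described in SAP 11.1 fall within that safety section.

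Neither population definition says what qualifies as a post-dose safety assessment.

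**The concern.** Belonging to the safety set depends on something that happens after dosing, and that event is related to the outcomes the safety tables measure. A subject must survive, or at least stay in contact, long enough to generate whatever record counts as an assessment. The usual reason for basing a safety set on exposure alone is to avoid this kind of selection.

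Two things are at stake. First, two programmers could apply the same sentence to the same data and build different safety sets, depending on whether they treat an adverse event or death record as an assessment. Second, the number of deaths in the ITT survival analysis might not reconcile with the number in the death summaries.

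**Working it through.** The plan gives no figure on this point, so the check compares the definitions and then works through illustrative denominators.

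**Step 1: the sets.** ITT = enrolled and dosed. Safety = enrolled and dosed and with at least one post-dose safety assessment. Safety is a subset of ITT, and is smaller whenever a dosed subject has no qualifying assessment.

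**Step 2: when that can occur.** Under Protocol 6.7.7 and Table 2, the first scheduled post-dose visit is Cycle 1 Day 8. The Table 2 window for Cycles 1 and 2 is ±3 days, so the visit falls on 8 − 3 = Day 5 to 8 + 3 = Day 11. CC-486 is self-administered (Protocol 8.7). A monotherapy subject who dies before that visit may have no scheduled post-dose assessment. A combination subject has vital signs taken during and after the Day 1 infusion (Protocol 6.6.1 and 8.2.2.2.3) and would qualify at once. The gap is therefore mainly in monotherapy.

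**Step 3: the two readings.** Let N be the cohort size, k the number of excluded subjects and d the deaths among retained subjects. The values of k and d are assumptions. N = 16 is the Stage 1 cohort size (SAP 4.3).

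Strict reading (a visit-based assessment is needed) and the k excluded subjects all died: ITT rate = (k + d)/N and safety-table rate = d/(N − k).

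| N | k | d | All dosed | Safety tables |
|---|---|---|---|---|
| 16 | 1 | 0 | 1/16 = 6.25% | 0/15 = 0% |
| 16 | 1 | 2 | 3/16 = 18.75% | 2/15 = 13.3% |
| 16 | 2 | 0 | 2/16 = 12.5% | 0/14 = 0% |
| 65 | 1 | 0 | 1/65 = 1.5% | 0/64 = 0% |

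The last row takes all 65 enrolled subjects as dosed.

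Broad reading (recorded adverse events and deaths qualify): the k excluded subjects have no post-dose information and add nothing to any numerator. All-dosed rate = d/N and safety-table rate = d/(N − k). With N = 16, k = 1 and d = 2, that is 2/16 = 12.5% against 2/15 = 13.3%. Here exclusion pushes the observed rate up.

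**Step 4: effect of the change.** With the extra condition removed, the safety set equals the ITT set as defined, k = 0, and each pair of rates coincides. The efficacy design is untouched because efficacy is analysed on ITT. An exact calculation of the two-stage rule (stop at 2 or fewer of 16, reject at 8 or more of 41) gives a type I error of 0.0995 and power of 0.801, in line with the stated 10% and 80%.

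**The case against.** The strongest reply is that a reported event is itself a safety assessment. Protocol 6.7 puts adverse events first in its list of safety assessments. Table 2 shows adverse event assessment as a continuous row starting at consent. A fatal adverse event is serious by definition (Protocol 11.2.1) and reportable within 24 hours (Protocol 11.1). A treatment-emergent event under SAP 11.1 needs only an onset on or after first dose, with no visit. On that reading most early deaths stay in the safety set. This is a reasonable interpretation, but neither document states it as the rule for the population, so the ambiguity stands.

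A reader might infer that an early death would vanish from the report. The documents do not support that. It would count in ITT overall survival. SAP 6 tabulates disposition for both ITT and safety, so a difference in numbers would be visible. The subject could also appear in the by-subject listing of deaths in SAP 11.1, since SAP 11 restricts summaries to the safety set and does not say the same of listings.

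A reader might also infer that withdrawal rates are biased downward. That does not follow either. Every dosed subject who stops treatment is due discontinuation procedures and at least 28 days of follow-up (Protocol 6.13 and 6.14), and ITT disposition counts withdrawals regardless.

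Finally, Protocol 6.3 asks for the first dose to be given at the site whenever possible, so the first exposure is not necessarily unobserved. That narrows the gap without closing it, because later doses are taken at home.

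**Conclusion.** The concern holds as a weakness of definition shared by both documents; it is not a contradiction between them. Membership depends on an undefined post-dosing event. Under the strict reading, a monotherapy subject who dies before the Day 8 visit can be missing from the treatment-emergent adverse event and death summaries while counting in ITT survival. Under the broad reading, the exclusions inflate rates slightly. The direction of bias is therefore not fixed.

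Its size cannot be estimated from the documents, which report no affected subject. The figures above show only what one or two exclusions would do in a small cohort. A reader might be tempted to apply the median survival of 4 to 6 months in Protocol 1.4.1 with a constant hazard: 1 − exp(−7 ln 2/(m × 30.4167)) gives 3.9% at m = 4 and 2.6% at m = 6, or 2.5 and 1.7 of 65 dying within 7 days. That is not an estimate of this problem. It counts all early deaths, not deaths with no safety record. It also applies a higher-risk median to a trial that admits lower-risk disease and excludes rapid progressors, and it includes combination subjects, who qualify on Day 1.

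The priority is low, but the wording should be settled.

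**What to change.** In Protocol 10.2.3 and SAP 5.2.3, define the safety population as all enrolled subjects who received at least one dose of any investigational product, with no condition on post-dose assessment. Add a listing of any dosed subject who has no post-dose assessment, giving vital status and the reason.

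The cost is one clause deleted in each document and one short listing. No new data are needed, and sample size, type I error and power do not change. A subject with no post-dose data would enter the denominators, so reported rates may move slightly in either direction. Change-from-baseline laboratory and vital-sign summaries still depend on which post-dose values exist.
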